# Aims for Phase I:

- 1. Develop a revised BIP manual for individual treatment delivery as a comparison treatment.
- 2. Develop a fidelity measure to distinguish F4C from BIP for therapist fidelity coding.
- 3. Establish acceptability and feasibility of F4C compared to traditional group BIP (BIP-G) and an individually delivered BIP (developed in aim 1 above; BIP-I). We will test the following specific research hypotheses:
  - i. Fathers randomized to F4C will have higher completion rates than those in either the BIP-I or BIP-G treatments.
  - ii. Fathers will report greater working alliance and satisfaction with F4C than either BIP condition
- 4. Assess initial intervention signal of F4C compared with BIP-I (developed in aim 1 above) and a group format BIP-G (current standard of care) program of comparable length. We will test the following specific research hypotheses:
  - i. Fathers receiving F4C will evidence greater improvement in reflective functioning (RF) and emotion regulation post-intervention compared to fathers receiving BIP-I or BIP-G.
  - ii. Fathers receiving F4C will show greater reductions in intimate partner violence (IPV) and child maltreatment (CM) over the 18 weeks of treatment compared to fathers receiving either BIP condition.
  - iii. Fathers receiving F4C will maintain reductions in IPV and CM in the 3 months following treatment.

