Why design an individual approach instead of group? Although programs for both IPV and CM have been implemented using a group approach F4C is an individual treatment approach. We chose this approach because: (1) IPV group approaches have been generally ineffective; (2) there is evidence that antisocial individuals in a group can have a contagion that limits the effectiveness of the group as a whole and may be iatrogenic; (3) interventions for aggressive adolescents were more effective delivered in an individual format compared to group; (4) the therapist needs to understand each client's own childhood history of exposure to violence, hostility triggers, and their intimate relationship patterns to optimally tailor role play, practice reflective functioning, and teach affect regulation skills; (5) our clinical experience with the population raises the concern that some men may be unwilling to share this information in group treatment; and (6) the co-parent and father-child focused components require the therapist to carefully assess RF, emotion dysregulation, and communication patterns based on the type of prior difficulties, whether the couple is still in a relationship, and the developmental age of the children in order to provide appropriate support. This is difficult in group treatment and does not allow for the individualized work and practice in session that is provided in F4C as one-on-one treatment.

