Phase I: Seventy five fathers of children aged 6 months to 11 years will be referred by the Department of Children and Families to the Parent and Family Development Program at Yale, recruited and randomized to either F4C BIP-I or BIP-G (n = 25 per group) following an initial screen and baseline assessment.

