# Treatment Phase.

Each treatment will be delivered weekly over 18 weeks. Male participants will meet online or be contacted via phone weekly with the RA to complete self-report assessments of IPV behaviors, father-child interactions and *substance use*. The RAs will be blind to the participants' treatment conditions. Study therapists will complete weekly session reports of session content and skill acquisitions based on completed homework.

*Fathers for Change*: F4C focuses on: 1) the fathering role to facilitate engagement, 2) RF to understand self, partner and children and emotion regulation skills to reduce IPV and child maltreatment F4C focuses on understanding of emotional experiences, how they impact thinking and behaviors related to partners, co-parents and children. F4C clients will meet individually with their F4C therapist for 50 minutes per week over 18 weeks.

**Batterer Intervention Program:** The BIP is a psychoeducational intervention that will be delivered in 50- minute individual sessions over 18 weeks. The intervention focuses on the impact of violence on victims, power and control tactics, and societal influences supporting men's violence toward women. The intervention includes didactics and experiential exercises including role plays to teach management skills. anger BIP is typically delivered in a group format, however will also be adapted to an individual Therapies will be delivered either in person or via format as part of the current study. secure/password protected zoom virtual sessions. All Yale safety protocols with regard to COVID-19 will be followed.

**Therapist Training.** Master's level clinicians will be trained to deliver the study interventions. [name] will utilize the therapist training manual, slides and videos generated from her pilot studies to train F4C therapists. She will meet weekly with F4C therapists for supervision. BIP-I and BIP-G therapists will be trained by [name] using the BIP manual and training materials modified for individual treatment delivery. BIP clinicians will meet weekly with [name] for supervision and intervention adherence.

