# Analytic Plan.

We will use Research Electronic Data Capture (REDCap™), a widely used secure web-based software package designed for clinical trials to collect study data.

Preliminary Analysis: A series of preliminary analyses will be conducted to: (1) characterize the sample, (2) document the internal reliability of measures, (3) check for logical consistency among related variables, (4) identify outlying values that should be considered for truncation, and (5) assess whether there are significant differences in outcomes based on study therapist. Although urn randomization procedures will be used to balance distribution of specific characteristics across treatment groups, we will explore between-group differences in urn variables and other demographics and possible moderators. Data analyses will be done independently and without

knowledge of group assignment, with the participant's group assignment anonymized to "treatment 1" or "treatment 2".

Phase I Hypotheses:

- i. Fathers randomized to F4C will have higher completion rates than those in the BIP-I or BIP-G treatment. Chi-square analysis will be used to examine between group differences in treatment completion.
- ii. Fathers will report greater working alliance and satisfaction with F4C than BIP-I or BIP-G. Analysis of variance will be used to test between group differences in working alliance and client satisfaction.
- iii. Fathers receiving F4C will evidence greater improvement in RF and emotion regulation, IPV, and child maltreatment(CM) compared with fathers receiving BIP-I or BIP-G postintervention. Mixed effects regression will be used to test for between-group differences in RF, emotion regulation, IPV, and CM representing treatment effects associated with F4C versus BIP over time. Separate IPV and CM sum scores will be created. Any instance of IPV or CM by any report (self, co-parent or current partner report on the Timeline Follow Back, child protection or arrest records) will be counted to create a sum score across reports. The Child Interactive Behavior Codes of Intrusiveness and Child Avoidance will be used as our observational measures of CM risk. Total coded RF score as measured by the PDI and self-reported emotion regulation on the DERS will be used to test impact mechanisms of F4C.

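### Only the BIP-G arm of Phase I is treated in shared therapy groups and no planned test allows for this, so contrasts with BIP-G will look too precise if outcomes correlate within groups

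*Combined protocol and SAP*

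**What the plan says.** The Research Plan (Section IV, item 3) has Phase I fathers "recruited and randomized to either F4C BIP-I or BIP-G (n = 25 per group"). The Phase I aims describe the third arm as "a group format BIP-G (current standard of care) program of comparable length". BIP-I is defined there as the individually delivered version, and under Treatment Phase "F4C clients will meet individually with their F4C therapist for 50 minutes per week over 18 weeks". One arm of three is therefore treated in shared groups.

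The Analytic Plan gives the tests under Phase I Hypotheses:

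- Hypothesis i: "Chi-square analysis will be used to examine between group differences in treatment completion".
- Hypothesis ii: "Analysis of variance will be used to test between group differences in working alliance and client satisfaction".
- Hypothesis iii: "Mixed effects regression will be used to test for between-group differences in RF, emotion regulation, IPV, and CM", described as effects over time. The random effects are not listed.

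The nearest provision is a preliminary analysis to "assess whether there are significant differences in outcomes based on study therapist". It concerns therapists, not therapy groups, and no consequence for the models is stated. Neither the analysis text nor the sample-size text (Section V, How was this estimate derived?) gives a therapy-group identifier, group size, number of groups, ICC or design effect.

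In the Background, the case for individual treatment includes evidence that "antisocial individuals in a group can have a contagion that limits the effectiveness of the group as a whole".

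**The concern.** Fathers who sit in the same group for a course of treatment share a leader, a group climate and each other. If this makes their outcomes alike, the BIP-G mean is less certain than that of 25 unrelated fathers, and an analysis that ignores the grouping reports too small a standard error. The other two arms do not have this feature, so the problem falls on contrasts with BIP-G. Those contrasts matter because the protocol says that the three arms are there to separate the effect of treatment format from that of content. An apparent advantage over BIP-G could then owe something to understated error.

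**Working it through.** **The plan's own figure.** The only Phase I precision figure is 80% power for d = 0.45 with 63 analysed fathers. The dropout step reproduces: 63/(1 - 0.16) = 75. The power does not, even before clustering. With 21 per arm, SE = sqrt(2/21) = 0.309 and 0.45/0.309 - 1.96 = -0.50, which gives 30.8% (two-sided 5% assumed). That is a separate matter and is noted only because it is the baseline here.

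**Inputs.** From the documents: 25 per arm, and only BIP-G grouped. Assumed: a two-sided 5% test, closed groups with fixed membership, three to five groups (m = 25/5 = 5 to 25/3 = 8.33 fathers each), and ICC 0.01 to 0.20.

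**Formulas.** The design effect in BIP-G is DE = 1 + (m - 1) x ICC. For F4C versus BIP-G the true-to-reported SE ratio is sqrt((1 + DE)/2). Type I error comes from 40,000 simulated t tests per cell, 25 independent fathers against 25 in groups.

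| ICC | 5 groups: DE | SE ratio | Type I error | 3 groups: DE | SE ratio | Type I error |
|---|---|---|---|---|---|---|
| 0.01 | 1.04 | 1.01 | 5.2% | 1.07 | 1.02 | 5.6% |
| 0.05 | 1.20 | 1.05 | 6.1% | 1.37 | 1.09 | 7.2% |
| 0.10 | 1.40 | 1.10 | 7.6% | 1.73 | 1.17 | 9.4% |
| 0.20 | 1.80 | 1.18 | 9.8% | 2.47 | 1.32 | 14.3% |

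At ICC 0 the simulation returns 5.0-5.1%, so the excess comes from the clustering. With four groups the results lie between the two columns. With two groups they are 5.7%, 8.7%, 12.0% and 18.6%.

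**Completion.** For an uncorrected pairwise chi-square, with 60% completion assumed, the error is 7.5-8.5% at ICC 0.05, 8.9-11.1% at 0.10 and 11.6-16.2% at 0.20 (five and three groups). This test already runs at about 6% without clustering at these sample sizes, so the excess should be read from 6%.

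**BIP arms pooled.** With F4C (25) against both BIP arms (50), the SE ratio is sqrt((1/25 + (1 + DE)/100)/(1/25 + 1/50)). At DE = 1.20 this is sqrt(0.062/0.060) = 1.02; at DE = 2.47 it is sqrt(0.0747/0.060) = 1.12. The simulated error is 5.3-5.6% at ICC 0.05, 5.8-6.4% at 0.10 and 6.4-7.9% at 0.20.

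**Power once clustering is counted.** With 21 per arm, SE = sqrt((1 + DE)/21). For m = 5 and ICC 0.05 (DE = 1.2), power falls from 30.8% to 28.4%. For m = 8 and ICC 0.10 (DE = 1.7) it falls to 24.0%.

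**The case against.** The strongest reply is that the documents do not show any inflation. They give no ICC, group size, number of groups or alpha, and do not say whether groups are closed or rolling. At ICC 0.01 the excess is negligible. This stands: a reader might infer that the false-positive rate does exceed 5%, but the documents support only the conditional statement.

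Second, a mixed model can carry a therapy-group effect, and its random effects are simply not listed. A reader might infer that hypothesis iii ignores the groups, but that rests on silence. The chi-square and the ordinary analysis of variance, however, assume independent fathers whatever the mixed model contains. The text also points to a Statistical Analysis section and a Statistical Design and Power Section that are not in what was reviewed. Those pointers attach to the exploratory mediation hypothesis and to power. If either section covers grouping, the sponsor can cite it.

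Third, the contagion passage can be over-read. It makes correlated outcomes within a group plausible. It does not say that the plan expects them, and it says nothing about dropout, so for completion the correlation is purely an assumption.

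Fourth, hypothesis iii speaks of F4C versus BIP over time, so the two BIP arms may be pooled, which at least roughly halves the excess. The listed hypotheses also include no BIP-I versus BIP-G test. Format is a stated purpose of the design, but such a test is not shown to be planned.

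Finally, Phase I is framed as feasibility, acceptability and an initial signal, and efficacy is left to Phase II. That limits the consequence but does not remove it.

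**Conclusion.** The point holds in conditional form. Only BIP-G is group-delivered, two of the three Phase I analyses treat fathers as independent outright, and the third states no therapy-group term. For any positive within-group correlation, an analysis that ignores the groups understates the error of contrasts with BIP-G. For an F4C versus BIP-G t test with 25 per arm and three to five closed groups, a nominal two-sided 5% becomes about 5-5.6%, 6-7%, 7-9% and 10-14% at ICC 0.01, 0.05, 0.10 and 0.20. With the BIP arms pooled it is about 5-8%. All of these rest on assumed ICCs and group structures.

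Two wider readings should be resisted. One is that the 25 BIP-G fathers are worth little more than the number of groups. The effective sample size, 25/DE, is 20.8, 17.9 and 13.9 with five groups and 18.3, 14.4 and 10.1 with three groups (ICC 0.05, 0.10, 0.20), well above three to five. The other is that the problem reaches F4C versus BIP-I or Phase II. In those comparisons both treatments are given individually, so this issue does not arise. The plan should be corrected, but the point does not undermine the trial's efficacy comparison.

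**What to change.** Record each BIP-G father's therapy group, and state the intended group size, the number of groups and an assumed ICC range.

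For the outcomes analysed as continuous (RF, emotion regulation, IPV, CM, alliance, satisfaction), analyse contrasts involving BIP-G with a partially nested model: a random group effect in BIP-G only, residual variance by arm, and Satterthwaite or Kenward-Roger degrees of freedom. Keep the group term whether or not it is significant. State whether the BIP arms are compared separately or pooled. In simulation, a test of this type brings the error back to about 4-7% with three to five groups.

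For completion, replace the plain chi-square with a cluster-adjusted comparison and a sensitivity analysis over the assumed ICC range. A mixed logistic model may not be stable with so few groups.

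The cost is one recorded identifier, revised analysis wording, and wider intervals with few degrees of freedom for contrasts with BIP-G. The correction has limits. With three to five groups, the estimated group variance is zero or negative in 46-49% of simulated trials at ICC 0.05 and 36-40% at 0.10, which is why the sensitivity analysis is also useful for the continuous outcomes. With only two groups the correction is incomplete. No change to treatment, visits or sample size is needed for this point.

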# Weekly and Monthly Measures During Treatment

The RA will meet with fathers via password protected zoom link or in person to complete logs of IPV, substance use and interactions with their children and monthly assessments of working alliance and treatment motivation via computerized survey at the time of their weekly clinical appointment. If fathers do not show for their appointment RAs will phone him to collect the information or email a secure survey. All data will be entered into a secure web-based REDCap database.

**TimeLine Follow-back-Spousal Violence, Child Maltreatment Risk, & Substance Use (TLFB-SV/SU/CM)** will be used to assess specific types of IPV (physical, sexual, psychological) toward partners on any given day, contact with the target child and child maltreatment risk behaviors (yelling, swearing, spanking, slapping, ignoring, harsh punishment). The TLFB-SV/SU/CM will be administered weekly to assess violence, substance use and CM risk behaviors during treatment. This is a reliable and valid instrument that has been used to assess relationship violence over time and links to substance use.  Participants, *the mother of their youngest child and if different their current female partner* will be asked to report IPV and CM throughout treatment.

**Measures of Treatment Targets:** Fathers will complete items from the Parental Acceptance Rejection Questionnaire, COPES and Unified Protocol Skill Use Scale to assess intervention coping skill use and emotion regulation/RF changes during treatment.

**Measures of Treatment Process:** Fathers will complete the **Working Alliance Inventory**,  **Motivation to Change** (85) on a monthly basis and the **Client Satisfaction Questionnaire** at the end of treatment to document (a) the quality of their relationship with their clinician, (b) their perceived motivation for change, and (c) satisfaction with treatment.

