# Phase I:

Seventy-five fathers of a biological child between 6 months and 11 years who are referred by the Department of Children and Families due to use of domestic violence in the last 12 months, the female co-parent of their youngest child and if different their current female intimate partners of more than 6 months, and their youngest biological child aged 6 months to11 years will participate for a total of up to 240 participants in this Phase 1B randomized controlled trial.

Female intimate partners who are not the co-parent of the youngest child will be contacted if they have been in a relationship with the father for at least 6 months at the time of consent.

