Collection of records from DCF and criminal records: Fathers will sign a release of information for collection of data from DCF related to his arrests for family violence related incidents and reports of IPV and child maltreatment to DCF. An excel spread sheet will be created that will include the names of study participants and their dates of birth. These will be sent to the contact person at DCF who will search records via a secure data transfer (encrypted and firewall protected using Yale's secure file transfer). The contact person who will be a state employee with approved access to the DCF and state arrest databases will search the names and dates of birth. The state employee will fill in the excel spread sheet with the data requested (number of reports to DCF for IPV and CM over the 26 weeks of treatment and number of IPV or CM related arrests over the 26 weeks of treatment). If an incident appears in both databases this will be noted to prevent double counting of a single incident of IPV multiple times due to reporting to both the police and DCF. The completed dataset will be returned to [name] via the same Yale secure file transfer. DCF will not keep any records of this data once transferred back to [name]. The excel sheet will then be updated by [name] with participant study ID numbers and the names and dates of birth will be deleted from the file. This ID only dataset will be saved for merging with other study data for analysis. This will ensure that arrest and DCF data will not be attached to participant names once it returns to Yale. The data will be stored on a password protected server only assessible by the study team.

4. If identifiers will be associated with the data and/or specimens, describe whether a record or list containing a code (i.e., code number, pseudonyms) will be used, where the list will be stored, who will have access to the list and when it will be destroyed.

The only file that will link the study participants to their study ID number will be an excel file kept on a password protected and encrypted computer in the PI's research lab. Only the PI and study RAs will have access to this file.

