Rating Scale and Questionnaires. Participants will be instructed that they can choose to skip any question or item if they do not want to answer. All the measures have been used in previous research with this population and in the pilot studies conducted by the PI or her co-investigators. The major disadvantage is the time taken to complete them. Our previous experience indicates that the baseline assessment will take 2 hours. A research assistant will meet with the participant online via zoom independent of their clinician and conduct all assessments. Only participants' code numbers will be recorded on the forms themselves to protect confidentiality. Also, careful efforts aimed at maintaining confidentiality have been effective in previous research, and only participants' code numbers will be recorded on the forms themselves to protect confidentiality. *The study team* (*Drs. [name] and [name]*) have extensive experience collecting IPV related data longitudinally from victims of IPV and have safely done so in previous studies. Procedures recommended in the literature and used in our prior studies of phone/text/email follow-up will be carefully adhered.

Additional Safety and Comfort: All research staff will receive substantial training and supervision to ensure that their interactions with all participants are not only professional, but also warm, friendly, non-confrontational, and respectful to all participants. We will take all precautions to ensure the safety of female co-parents of our male participants including: a) ensuring that partners' responses to all screening items are confidential from one another; b) allowing a male participant to remain in the study even if his female partner declines participation for herself or the child (he will not be informed of her decision instead he will be told the research team has decided to continue

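### Phase I hypothesis iii sums IPV and CM reports across informants and records, with no rule for counting one incident once

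*Combined protocol and SAP*

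**What the plan says.** The scoring rule is in the Analytic Plan, Phase I Hypotheses, item iii. It begins "Any instance of IPV or CM by any report", lists the sources as "self, co-parent or current partner report on the Timeline Follow Back, child protection or arrest records", and says that these "will be counted to create a sum score across reports". IPV and CM are scored separately. The item plans a mixed effects regression but states no way of matching one incident across sources and no allowance for how many people reported or for how many weeks.

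Four other places bear on the rule:

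- **Records.** Section VI, item 3: "If an incident appears in both databases this will be noted to prevent double counting of a single incident of IPV multiple times", and the reason given is "due to reporting to both the police and DCF". The agency is to return totals of reports and of arrests. No incident dates are listed.
- **Calendars.** Weekly and Monthly Measures During Treatment describes a Timeline Follow-back that records types of IPV "toward partners on any given day", so it resolves events to the day.
- **Third informant.** Participant Population, Phase I, adds current partners only "if different their current female intimate partners of more than 6 months".
- **Refusal.** Section VII, item 2, provides for "allowing a male participant to remain in the study even if his female partner declines participation for herself or the child". The Exclusion Criteria remove a father whose co-parent will not give information on the child's symptoms. The two provisions need to be reconciled, but that criterion concerns the child's symptoms and does not guarantee weekly violence calendars.

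**The concern.** A score that adds reports measures two things at once: how much violence occurred and how many people reported it. An incident logged by the father and by the co-parent that also led to an arrest would contribute 3. The same incident in a family where only the father reports would contribute 1. The item iii comparison of F4C with the two BIP arms would then carry this reporting component. The exploratory mediation hypothesis (item iv) names the same two outcomes.

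If the mix of informants is the same in every arm, the result is extra noise between fathers. If co-parents or partners report more completely in one arm, that arm looks more violent for the same conduct. The direction cannot be known in advance.

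**Working it through.** The plan states no figure for this score, so there is nothing to reproduce. The check compares the rules and then illustrates their consequence.

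**Which pairs of sources have a de-duplication rule**

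| Pair of sources | Rule in the documents |
|---|---|
| Child protection v arrest records | Yes (Section VI, item 3), worded for IPV |
| Father v co-parent v partner calendars | None |
| Calendars v records | None; records are described as totals without dates |

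**Score per true incident.** Assume each of k informants reports a true incident independently with probability p.

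- Reports added: k × p.
- Each incident counted once: 1 − (1 − p)^k.

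All values of p are assumptions.

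| p | Added, k = 1 / 2 / 3 | Counted once, k = 1 / 2 / 3 |
|---|---|---|
| 0.3 | 0.30 / 0.60 / 0.90 | 0.30 / 0.51 / 0.66 |
| 0.5 | 0.50 / 1.00 / 1.50 | 0.50 / 0.75 / 0.88 |
| 0.6 | 0.60 / 1.20 / 1.80 | 0.60 / 0.84 / 0.94 |
| 0.7 | 0.70 / 1.40 / 2.10 | 0.70 / 0.91 / 0.97 |
| 0.9 | 0.90 / 1.80 / 2.70 | 0.90 / 0.99 / 1.00 |

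When reports are added, the score triples from one to three informants at any p. Counting once narrows the range but does not close it unless p is high.

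**Arm ratio under equal violence, scenario A.** Assume the father is always an informant, there is no current partner, the co-parent is an informant for 80% of one arm and 60% of the other, and p = 0.6.

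- Added: (0.6 + 0.8 × 0.6) / (0.6 + 0.6 × 0.6) = 1.08 / 0.96 = 1.125. Here p cancels, leaving 1.8 / 1.6.
- Counted once: (0.8 × 0.84 + 0.2 × 0.60) / (0.6 × 0.84 + 0.4 × 0.60) = 0.792 / 0.744 = 1.065.

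**Scenario B.** Assume the father is always an informant, 20% of both arms have a current partner who is a separate informant, and the co-parent is an informant for 90% v 70%.

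- Added: (1 + 0.9 + 0.2) / (1 + 0.7 + 0.2) = 2.1 / 1.9 = 1.105 at any p.
- Counted once: 1.082, 1.064, 1.042 and 1.015 at p = 0.3, 0.5, 0.7 and 0.9.

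In scenario A about half of the excess (0.065 of 0.125) remains after de-duplication. That part comes from missing informants, not from multiple counting.

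**The case against.** **The text can be read the other way.** "Any instance of IPV or CM by any report" may mean that an incident counts once if anyone reports it, and Section VI shows that the authors want to avoid double counting. This stands as far as it goes: a reader might infer that multiple counting is certain, and the documents do not establish that. But summing across reports points the other way, and two analysts could build different outcomes from the same sentence.

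**Scope.** The rule appears only under Phase I, which seeks an initial signal in 75 fathers. Measures during baseline names the masked FSI-R rating, which compiles several sources, as the primary outcome measure, and the Phase II Aim 1 analysis does not invoke the sum score. A reader might infer that the trial's main efficacy result is affected; the documents do not support that. Hypothesis iii, however, does not mention the FSI-R, so the FSI-R does not repair the scores tested there.

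**Differential reporting is not shown.** A reader might infer that F4C raises co-parent reporting because co-parents attend its sessions. The Background lists four co-parent topics within individual therapy sessions, and Treatment Phase has the father meeting his therapist individually; neither says that co-parents attend. Nor does the hypothesised difference in fathers' completion imply different co-parent reporting. Research staff contact mothers directly without telling fathers, and co-parents are paid $5 per weekly log. An arm difference in reporting is therefore possible but not documented.

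**Adjustment can do harm.** Conditioning on which informants reported uses a variable that arises after randomisation and could itself bias the comparison. This stands and limits the remedy.

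**Conclusion.** The point holds for the Phase I IPV and CM sum scores. Taken literally, the rule lets one incident count once per reporter and makes the score depend on a number of informants that varies by family. The existing safeguard covers only child protection against police records, and only in words about IPV.

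No size of bias can be derived from the documents. The ratios of 1.125 (added) and 1.065 (counted once) rest on independent reporting, p = 0.6 and a co-parent split of 80% v 60%, all assumed. With equal reporting across arms the arm ratio under equal violence is 1, and only noise is added. Treating 12.5% as the expected bias, or supposing that de-duplication alone would cure it, goes further than the evidence.

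**What to change.** 1. Replace the sum with a count of distinct incidents. Match the three calendars on father, calendar date and type of behaviour (IPV or CM), so that an incident-day reported by any informant counts once.
2. Extend the Section VI record rule to CM.
3. Ask the agency for incident dates so that records can be matched to calendars. If dates cannot be had, analyse records as a separate outcome and do not add them to the calendar count.
4. Analyse the count with an offset for weeks with reports.
5. Report informant-specific counts by arm (for example father only and co-parent only) as a sensitivity analysis. Do not adjust the main comparison for which informants reported.

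**Cost.** Plan wording, a data-management rule and a small change to the agency data request. The calendars already resolve to the day, so matching them needs no new collection. The downsides are that several incidents of the same type on one day count as one, and that some dependence on missing informants remains, which item 5 is meant to expose.
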